1.0	09/Nov/2017	[name]	Clinical Writer – This is the initial version.

LIST OF ABBREVIATIONS AND TERMS

2D	Two dimensional
3D	Three dimensional
AE	Adverse Event
ADE	Adverse Device Effect
ALARP	As Low as Reasonably Practicable
CA	Competent Authority
CAPM	GE Clinical Affairs Project Manager
CC	Craniocaudal
CCG	Case Report Form Completion Guidelines
CFR	Code of Federal Regulations
CHF	Clinical History File (synonymous with e-Trial Master File)
CRF	Case Report Form
DBT	Digital Breast Tomosynthesis
EC	Ethics Committee
eCRF	Electronic case report form
FDA	United States Food and Drug Administration
FFDM	Full-field Digital Mammography
GCP	Good Clinical Practice (see ISO 14155:2011) ¹
GE	General Electric
GEHC	General Electric Healthcare
Guidance	Guidance for Industry and FDA Staff - Class II Special Controls Guidance Document: Full-Field Digital Mammography System (2012)
ICF	Informed Consent Form
ISO	International Standards Organization
MLO	Mediolateral Oblique
MQSA	Mammography Quality Standards Act
MWS	GE MyWorkshop Internal Documentation System
PAC	Patient-assisted Compression
PI	Principal Investigator
Reader	Interpreting Physician, as defined under U.S. FDA 21CFR §900.12(a)(1)(i)(B)(2)
SADE	Serious Adverse Device Effect
SAE	Serious Adverse Event
TC	Technologist-controlled
U.S.	United States
USADE	Unexpected Serious Adverse Device Effect

STUDY SYNOPSIS

Sponsor:	General Electric Company, acting through its GE Healthcare Business
Research Type:	This is a Clinical, single-blind, randomized, prospective research study.
Regulatory Status:	
This is a pre-market research study of the following products:
 
Post-market: Patient-assisted Compression (PAC) on Senographe Pristina 3D (Senographe Pristina FFDM with PAC is FDA-cleared; thus, PAC is being used off-label for the purposes of this DBT-focused study, indicating the pre-market nature of the research.)
 
Technologist-controlled compression on Senographe Pristina 3D

Background and Rationale:	Patient-assisted compression (PAC) allows the patient to participate in controlling the amount of compression force during mammography and is a personalized approach that has demonstrated successful reduction in discomfort experienced during mammography. GE Healthcare's Senographe Pristina, an innovative mammography platform that provides both two-dimensional (2D) and three-dimensional (3D) imaging capabilities, offers both standard and patient-assisted compression modes. This study will evaluate image quality and clinical workflow as it relates to use of PAC with the Senographe Pristina 3D. Study are intended to support regulatory submissions.
Procedures/Methods:	
The study population will consist of adult asymptomatic women presenting for screening 2D mammography. One breast of each subject will be identified as the “breast of interest,” which will undergo study-specific 3D imaging consisting of two-view (craniocaudal and mediolateral oblique) PA compression and image acquisition, followed by two-view technologist-controlled (TC) compression and image acquisition. The breast of interest will be randomly assigned to either the first breast imaged during the exam or the second breast imaged. TC compression and imaging, and procedures performed on the subject’s other breast will be conducted per standard of care.
 
Following image acquisition, 3D image quality evaluation will be conducted by MQSA-qualified readers. Prior to the reading session, images will be de-identified and the following information will be removed from the DICOM header to blind readers to the compression mode used during acquisition: time stamp, compression force, and breast thickness. The image sets will also be randomized for presentation during the image attribute reviews. Two (2) readers will evaluate each PAC and TC compression image set collected from each subject’s breast of interest and assess the acceptability of image attributes, as defined in the Guidance for Industry and FDA Staff - Class II Special Controls Guidance Document: Full-Field Digital Mammography System (2012). A third reader will provide adjudication, if there is disagreement for a given image set’s overall clinical image quality.
 
Workflow data, including the incidence of technologist intervention during acquisition and need for repeat image acquisition, will also be collected.
 
The proportion of PAC image sets that are of equal or higher acceptability than TC image sets will be calculated. A 95% confidence interval will be calculated using asymptotic method with continuity correction. The proportion of image sets indicated for repeated

	
image acquisition when using PA mode or TC mode will be summarized. Other endpoint data will be summarized using descriptive statistics. No statistical hypothesis is being tested in this study.

Objectives:	
The primary objective is to compare the acceptability of overall image quality in unilateral two-view (CC and MLO) breast images acquired using PAC and TC compression modes.
 
The secondary objectives are:
 
 • To evaluate the need for repeat image acquisition when using PAC and TC compression modes; and • To evaluate acceptability of mammographic attributes for unilateral two-view breast images acquired using PAC and TC compression modes, per the Guidance for Industry and FDA Staff - Class II Special Controls Guidance Document: Full-Field Digital Mammography System (2012). 
The exploratory objectives are:
 
 • To collect workflow data for PAC and TC compression, and • To collect breast thickness, radiation dose, and compression force for images acquired using PAC and TC compression. 
The safety objective is to collect safety information, including adverse events (AEs), serious adverse events (SAEs), and product issues.

Endpoints:	
The primary endpoint is the overall image quality acceptability on a per subject-basis using a binary response of either acceptable or unacceptable for unilateral, two-view PAC and TC compression image sets.
 
The secondary endpoints are:
 
 • Number of incidences per image set when the technologist and/or readers indicate a repeat acquisition for PAC and TC compression; and • Acceptability of mammographic attributes, as defined in the Guidance and as described in this protocol. 
The exploratory endpoints will be collected per subject for each study-specific 3D PAC and TC compression. The endpoints are:
 
 • Type and incidence of technologist interventions (e.g. technologist uses footswitch to increase compression); and • Breast thickness, radiation dose, and compression force. 
The safety endpoints are the type and number of AEs, SAEs, and device issues.

Eligibility criteria:	
 1) Are women aged 40 years or older; 2) Are asymptomatic and scheduled for screening mammography; 3) Have left and right breasts; 4) Have breast sizes compatible with the dimensions of a 24 x 31 cm image detector, without anatomical cut-off; 5) Are documented as non-pregnant based on the investigator's medical judgment and in consideration of local clinical practice standards for evidence of non-pregnancy; 6) Are able and willing to comply with study procedures; and 7) Are able and willing to provide written informed consent to participate. 	
 1) Have been previously included in this study or are participating in another study expected to interfere with study procedures or outcomes; 2) Participated in the GE Healthcare study that investigated PAC with the Senographe Pristina FFDM system (Study Number: 124.03-2017-GES-0002; Study Title: Patient-Assisted Compression – Impact on Image Quality and Workflow); 3) Have undergone diagnostic or surgical intervention(s) or procedure(s) on either breast, including breast biopsy, lumpectomy, or reconstruction, within five (5) years (≤ 5 years) of the study exam date; 4) Are currently undergoing radiotherapy or chemotherapy, or have a history of prior radiotherapy treatment on either breast; 5) Are currently lactating; or 6) Have breast implants.
Sample size and Sites:	Up to 36 subjects from one (1) site will be included as part of this study to achieve the targeted number of complete and evaluable subjects. The target sample size for this study is 30 subjects, providing 60 evaluable 3D image sets for the image attribute review (30 PAC image sets and 30 TC compression image sets). The number of subjects was determined based on Sponsor discussions with a U.S. FDA Medical Officer, who indicated that, during MQSA re-accreditation, sites are requested to submit sample images. If an issue is identified with the sample images, an Advanced Mammographic Review occurs, where the quality of 30 images is assessed to determine whether the issue was isolated or systemic.	
Study duration:	The study is expected to last approximately three (3) months.	

ADMINISTRATIVE STRUCTURE OF INVESTIGATION

Clinical Affairs Project Manager (Sponsor Contact):	[name] Tel: [name] e-mail: [contact]	GE Healthcare (GEHC) Address: [name] [name] U.S.

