1.2 Controls and Minimization of Bias

Due to the inherent difference in utility of standard and PAC modes, study subjects and study staff will not be blinded to the compression mode. However, the following bias control methods will be employed in this study:

- Selection bias will be limited by consecutively enrolling eligible subjects.
- Spectrum bias will be limited by using a population expected to represent the general population at the investigational site, without regard to race or ethnicity.
- PAC will be randomly assigned to either the first or second breast imaged to mitigate subject-learning bias associated with the amount of compression required for image acquisition.
- Reading order bias will be limited by randomizing the order of image set presentation to the readers.
- Readers conducting image quality evaluations will be blinded to the compression mode used to obtain the images.
- A minimum of three (3) radiology technologists will conduct the study procedures to mitigate bias introduced by technologist-specific practices.

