3.1.1 Primary Objective

The primary objective is to compare the acceptability of overall image quality in unilateral two-view (CC and MLO) breast images acquired using PAC and TC compression modes.

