4.6 Breast of Interest Randomization

One (1) breast per subject will undergo study-specific procedures (hereafter referred to as “breast of interest”) while the second breast will be imaged per standard of care. The breast of interest will be randomized across all subjects so that approximately half the subjects will be assigned to the first imaged breast and the other half will be assigned to the second imaged breast (Figure 2).

Site technologists conducting the study will perform each subject’s mammography exam per standard practice. Thus, the laterality of the breast of interest will solely depend on which breast (left or right) the technologist images first and second in standard practice.

[figure not shown]

Figure 2 – Schematic showing image acquisitions based on the randomly-assigned breast of interest (i.e. first or second breast).

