5.3 Description of Study Procedures

5.3.1 Image acquisitions

Each subject will undergo her regularly scheduled breast imaging exam per standard practices at the investigational site, with the exception of the study-specific image acquisitions using PAC. The site uses combo mode (2D and 3D imaging) for screening mammography, and does not decompress between 3D and 2D imaging for a given view. Additionally, 3D acquisitions are conducted first per standard of practice. Thus, the sequence of imaging procedures will be conducted for the breast of interest, as shown in Figure 4. There shall be no repeat imaging administered using PAC mode, and standard of care will be used for imaging of the subject's other breast.

[figure not shown]

Figure 4 – Sequence of imaging procedures for the breast of interest (dark boxes = PAC, study-specific imaging, white boxes = standard of care (SoC) at the site).

A minimum of three (3) site technologists will perform the image acquisitions and related study procedures. Study procedures shall not impact the order in which the left and right breasts are imaged during the subjects' exams.

There will be two (2) study-specific image sets of the breast of interest for each subject. Image sets will consist of CC and MLO views obtained using PAC and CC and MLO views obtained using TC compression.

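### PAC always precedes TC on the breast of interest, so the PAC–TC contrast is confounded with first-versus-second acquisition on that breast

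*Combined protocol and SAP*

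**What the plan says.** The Study Synopsis (Procedures/Methods) states that two-view PAC imaging of the breast of interest is "followed by two-view technologist-controlled (TC) compression and image acquisition". Section 5.3.1 describes a single sequence for that breast: "Thus, the sequence of imaging procedures will be conducted for the breast of interest, as shown in Figure 4". No text gives a reverse order or counterbalances the two modes.

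What is randomised is the breast. The synopsis says it is "randomly assigned to either the first breast imaged during the exam or the second breast imaged", and Section 4.6 expects that "approximately half the subjects will be assigned to the first imaged breast and the other half will be assigned to the second imaged breast". Section 1.2 gives the purpose: "PAC will be randomly assigned to either the first or second breast imaged to mitigate subject-learning bias". Section 1.2 also states that "Reading order bias will be limited by randomizing the order of image set presentation to the readers", and that readers are blinded to mode.

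The primary objective (Section 3.1.1) is to "compare the acceptability of overall image quality in unilateral two-view (CC and MLO) breast images" between the two modes. The primary statistic (Section 10.3.2) is the proportion of subjects whose PAC set is rated at least as acceptable as the TC set. It is repeated by first/second breast, and acceptability is also reported for each mode separately. Section 10.3.3 repeats the breast-order subgroups for repeat acquisition and compression force. Section 10.1 states that no hypothesis is tested.

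**The concern.** The comparison is within one breast, and the two modes always occupy the same positions in the sequence. Anything that differs between a first and a second acquisition of the same breast is carried entirely by the mode contrast. Candidates are tissue that has already been compressed, positioning refined on a second attempt, and tolerance or motion during a further compression. These are possibilities; the documents do not report any of them as an observed effect.

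What is at stake is attribution. Section 3.1 says the results are meant to support regulatory submissions for PAC on the 3D system. An observed PAC–TC difference, or its absence, in acceptability, repeat need, force, thickness or dose could reflect mode, position or both. The bias could count against PAC, favour it, or hide a real difference. Because the study is descriptive, the consequence is a biased estimate and not an inflated type I error.

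**Working it through.** **1. The plan's own figure.** Section 10.2 gives a 95% interval no wider than 13% at a proportion of 95% with 30 pairs. The half-width is 1.96 × √(0.95 × 0.05 / 30) = 0.078. This gives 87.2% to 100% once the upper limit is cut at 100%, a width of 12.8%. The figure is thus reproduced without the continuity correction; with the planned correction of 1/60 the truncated width is 14.5%. That mismatch is a separate matter. What matters here is that the width measures sampling error only and contains no allowance for an order effect.

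**2. Which safeguard acts on what.**

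| Safeguard | Source | Separates mode from within-breast order? |
|---|---|---|
| Breast of interest randomised to first or second | Sections 1.2, 4.6 | No: PAC precedes TC in both groups |
| Subgroups by that assignment | Sections 10.3.2, 10.3.3 | No, for the same reason |
| Randomised presentation, blinded readers | Sections 1.2, 5.3.2 | No: these act on reading, not acquisition |
| At least three technologists | Sections 1.2, 5.3.1 | No: all follow the same order |

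Mode and position are therefore perfectly collinear in 30 of 30 planned pairs.

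**3. Illustration of size.** The 95% is borrowed from Section 10.2, where it is the planning value for the paired proportion, and is assumed here as the acceptability of a second acquisition. Further assumptions, not in the documents: no true mode effect, independent ratings within a subject, and a first acquisition worse by d = 2, 5 or 8 points.

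For binary ratings, P(PAC ≥ TC) = 1 − P(PAC unacceptable and TC acceptable) = 1 − (1 − p_PAC) × p_TC. With no order effect this is 1 − 0.05 × 0.95 = 0.9525.

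| d | PAC then TC | TC then PAC | 1:1 average |
|---|---|---|---|
| 2 | 1 − 0.07 × 0.95 = 0.9335 | 1 − 0.05 × 0.93 = 0.9535 | 0.9435 |
| 5 | 1 − 0.10 × 0.95 = 0.9050 | 1 − 0.05 × 0.90 = 0.9550 | 0.9300 |
| 8 | 1 − 0.13 × 0.95 = 0.8765 | 1 − 0.05 × 0.87 = 0.9565 | 0.9165 |

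- PAC–TC difference: −2, −5 or −8 points under the fixed order; 0 in expectation under 1:1.
- Shift of the paired proportion from 95.25%: 1.9, 4.75 or 7.6 points under the fixed order; 0.9, 2.25 or 3.6 points under 1:1. Balancing removes about half.

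The remainder stays because the paired proportion counts only pairs with PAC unacceptable and TC acceptable. Balancing makes discordance equal in the two directions, but it does not restore the acceptability lost by whichever set was acquired first.

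**4. Direction and masking.** If the second acquisition is instead 5 points worse (0.95 then 0.90), the difference is +5 points and the paired proportion 0.955, which favours PAC. A true PAC deficit of 5 points combined with a 5-point second-position loss gives 0.90 − 0.90 = 0 under the fixed order. Under a balanced order it shows as −5.

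**5. Prior experience of TC.** Assume the other breast is imaged with TC, the standard mode (Section 2.4), and that one breast is finished before the other begins. At present TC precedes PAC in the exam only when the breast of interest is second, in about 50% of subjects. With four equal cells it precedes PAC in three of them, about 75%.

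**The case against.** The strongest reply has four parts.

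- **No order effect is shown.** The documents give neither size nor direction, and 2 to 8 points is only 0.6 to 2.4 subjects in 30, against a plain half-width of about 8 points. Two image sets of one breast in one exam are unlikely to be rated independently. This stands as a limit on the illustration: the paired-proportion levels depend on independence, although the bias in the difference does not. It does not remove the collinearity, and an interval does not reflect bias.
- **The study is descriptive, and PAC acceptability is reported on its own.** This stands. The PAC proportion does not use the TC contrast, and it comes from PAC as the first mode applied to that breast. A reader might infer that the study says nothing about PAC image quality; the documents do not support that.
- **Balancing has a price.** It raises prior experience of TC from about 50% to about 75% of subjects, which works against the subject-learning control in Section 1.2. Results by sequence would rest on about 15 subjects each, with 15 × 0.05 = 0.75 unacceptable sets expected per mode at 95%. This stands as a trade-off to be declared.
- **Figure 4 is not shown.** The modes may alternate view by view, so that PAC precedes TC within each view and the PAC MLO view follows the TC CC view. The synopsis still puts PAC before TC, but the exact form of the confounding cannot be settled.

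A reader might also suppose that PAC goes first to stop subjects imitating TC compression. The documents give no reason for the order.

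**Conclusion.** The concern holds for the PAC–TC contrast. In every planned pair, mode is inseparable from first-versus-second acquisition on the breast of interest, and no planned analysis can separate them. This follows from the text and needs no numerical assumption beyond reading the synopsis order as applying to all subjects.

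The size is unknown. The 2-, 5- and 8-point cases show how an order effect would pass through to the results; they do not estimate one.

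Two stronger readings should be resisted. One is that an order effect has been shown to disadvantage PAC: the direction is open. The other is that a balanced sequence would remove the whole effect from the primary statistic: it zeroes the expected PAC–TC difference but recovers only about half of the shift in the paired proportion. The point is a worthwhile design improvement, and failing that a limitation to state. It does not invalidate the study.

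**What to change.** **Preferred.** Randomise the within-breast sequence (PAC then TC, or TC then PAC) 1:1 within the existing first/second-breast assignment. Report both the PAC–TC difference in acceptability and the primary proportion, overall and by sequence. The difference needs to be added because it is the quantity that balancing protects. Cost: a four-cell randomisation list and a protocol amendment, with no added subjects, images or exposures. Declare the downsides: more subjects with prior experience of TC, and sparse by-sequence results.

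**If the fixed order stays.** Extract force, thickness and dose from the DICOM headers of the other breast and compare within subject:

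- (a) TC on the other breast with TC on the breast of interest, to estimate the effect of a preceding PAC compression of the same breast;
- (b) PAC on the breast of interest with TC on the other breast, each being the first compression of its breast.

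Because breast order is randomised, both comparisons are balanced in expectation for breast position and side. State that experience of PAC or TC carried across from the other breast remains, and that these comparisons do not repair the image-acceptability contrast. Describe the primary result as PAC-first versus TC-second. Cost: extra header data, one table, and a short protocol change, since Section 3.2.3 limits the exploratory endpoints to study-specific imaging.

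In either case, state in the text whether Figure 4 runs the modes by set or by view.

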1. BACKGROUND AND JUSTIFICATION

1.1 Screening Mammography and Patient-Assisted Compression

Leading authorities on breast cancer recommend regular screening mammography for women aged 40 years and older as a means of early detection for breast cancer, leading to increased survival rates and more treatment options.^{2, 3, 4} Numerous randomized trials have demonstrated that regular mammographic screening reduces breast cancer mortality,^{5, 6, 7, 8, 9} with more than 40% reduction in breast cancer deaths.^{10, 11} Amidst the success of screening mammography, clinicians struggle to maintain patient participation in regular screening programs. Notably, a systematic review by Whelehan, et al. concluded that pain experienced during screening mammography (e.g. compression pain) contributed to reduced rates of repeat participation in regular screening programs.¹²

Adequate breast compression during mammography creates uniform thickness and flattens tissues,⁴ which is necessary to obtain sufficient image quality^{4, 13, 14} and reduce radiation dose.^{4, 15} Various methods are being investigated to maintain sufficient compression while reducing pain/discomfort associated with mammography. Specifically, studies have shown that a personalized approach to compression can significantly reduce pain intensity and discomfort experienced by patients while maintaining diagnostic image quality.^{16, 17, 18}

Patient-assisted compression (PAC) allows the patient to control the amount of compression force during mammography and is a personalized approach that has demonstrated successful pain reduction in mammography.¹⁶ GE Healthcare's Senographe Pristina, an innovative mammography platform that provides both two-dimensional (2D) and three-dimensional (3D) imaging capabilities, offers standard and patient-assisted compression modes. The study described herein is being conducted to compare the image quality of DBT breast images obtained using standard (i.e. technologist-controlled) compression and PAC in an asymptomatic female population undergoing 2D and 3D (i.e. "combo mode") screening mammography. PAC, which is marketed as Pristina Dueta™ in some countries, was recently cleared by the U.S. FDA for use with Senographe Pristina FFDM (2D) system and is the first of its kind in the medical device industry. This study will evaluate image quality and clinical workflow as it relates to use of PAC with the Senographe Pristina 3D (DBT option). Study results are intended to support regulatory submissions.

